7.1.2 Sample size calculation

This trial requires the test group: ① the non-inferiority comparison with the control groups is established and the next statistical test is carried out; ② when the absolute criteria of SCR and SPR are achieved, the trial can be considered as successful and a positive conclusion can be drawn for the test group. In this trial, when evaluating between the test group 1 (0.25-mL QIV) and test group 2 (0.5mL-QIV), the strategy of sequential test is adopted. First, test group 2 is evaluated. If the positive conclusion of test group 2 is established, test group 1 is further evaluated. Therefore, class I error correction is no longer carried out. The sample size of phase III clinical trials is estimated first by non-inferiority design, namely the QIV group is non-inferior to the TIV group. The primary endpoints of this study include two indicators: SCR and GMT. Only when the SCR and GMT of four serotypes in test group are non-inferior to the control vaccine, the investigational vaccine is considered to be non-inferior to the control vaccine. The total power is 80%, the type II

error is 0.2. Based on the different sample size requirements of the two indicators, the type II error is allocated, with 0.16 for seroconversion rate comparison and 0.04 for GMT comparison.

(1) Calculation of sample size with the SCR as the indicator:

According to the results of the previous Anflu phase IV clinical trial and other literature, the SCR of the types contained in the vaccine 28 days after vaccination is over 65%, which is used as the reference proportion to estimate the sample size. The test level is taken as one-sided $\alpha=0.025$, the power of non-inferiority comparison for the seroconversion rate of a serotype is taken as $1-\beta_1/4=1-0.16/4=96\%$, and the non-inferiority threshold Δ is taken as -10%. When comparing the non-inferiority of BY or BV strain, NT:NC=2:1, and PASS software is used to calculate the sample size, the test group needs 914 samples and the control group needs 457 samples. When the non-inferiority test of H1N1 or H3N2 strain is carried out, two control groups are pooled. The sample size ratio of the test group and the pooled control group is 1:1, and the test group and the pooled control group need 625 participants.

(2) Calculation of sample size with the GMT as the indicator:

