3.1 Objective

3.1.1 Primary Objective

- To evaluate the non-inferiority of immunogenicity in participants aged 6-35 months after 2 doses of 0.5mL quadrivalent influenza vaccine (0.5mL-dose QIV) compared with two trivalent influenza vaccines (TIVs, including BV or BY) for the shared strains, in terms of seroconversion rate (SCR) and Geometric mean titer (GMT) for HI antibody;
- To evaluate the non-inferiority of immunogenicity in participants aged 6-35 months after 2 doses of 0.25mL quadrivalent influenza vaccine (0.25mL-dose QIV) compared with two trivalent influenza vaccines (including BV or BY) for the shared strains, in terms of SCR and GMT for HI antibody;
- To evaluate the absolute criteria of HI antibody SCR and seroprotection rate (SPR) for each strain specified in the protocol in participants aged 6-35 months after two doses of 0.25mL-dose or 0.5mL-dose QIVs.

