4.3 Sample Size

This trial requires the test group: ① the non-inferiority comparison with the control groups is established and the next statistical test is carried out; ② when the absolute criteria of SCR and SPR are achieved, the trial can be considered as successful and a positive conclusion can be drawn for the test group. In this trial, when evaluating between the test group 1 (0.25-mL QIV) and test group 2 (0.5mL-QIV), the strategy of sequential test is adopted. First, test group 2 is evaluated. If the positive conclusion of test group 2 is established, test group 1 is further evaluated. Therefore, class I error correction is no longer carried out. The sample size of phase III clinical trials is estimated first by non-inferiority design, namely the QIV group is non-inferior to the TIV group. The primary endpoints of this study include two indicators: SCR and GMT. Only when the SCR and GMT of four serotypes in test group are non-inferior to the control vaccine, the investigational vaccine is considered to be non-inferior to the control vaccine. The total power is 80%, the type II error is 0.2. Based on the different sample size requirements of the two indicators, the type II error is allocated, with 0.16 for SCR comparison and 0.04 for GMT comparison.

(1) Calculation of sample size with the SCR as the indicator:

According to the results of the previous Anflu phase IV clinical trial and other literature, the SCR of the types contained in the vaccine 28 days after vaccination is over 65%, which is used as the reference proportion to estimate the sample size. The test level is taken as one-sided $\alpha=0.025$, the power of non-inferiority comparison for the SCR of a serotype is taken as $1-\beta1/4=1-0.16/4=96\%$, and the non-inferiority threshold Δ is taken as -10%. When comparing the non-inferiority of BY or BV strain, NT:NC=2:1, and PASS software is used to calculate the sample size, the test group needs 914 samples and the control group needs 457 samples. When the non-inferiority test of H1N1 or H3N2 strain is carried out, two control groups are pooled. The sample size ratio of the test group and the pooled control group is 1:1, and the test group and the pooled control group need 625 participants.

(2) Calculation of sample size with the GMT as the indicator:

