- ✓ If the lower limit of the two-sided 95%CI of SCR difference for 28d post-total vaccination serum HI antibody between the two groups (test group 1-pooled control group) and (test group 2-pooled control group) for this type is $\geq -10\%$, the post-vaccination SCR of the test group for this type can be considered to be non-inferior to that of the pooled control group. Otherwise, the non-inferiority test is considered to have failed.

✧ Analysis of post-vaccination antibody SPR

The post-vaccination antibody SPR in all populations, 28d post-total vaccination serum HI SPR in the susceptible population, and the 28d post-total vaccination serum HI SPR in the non-susceptible population, and the 28d post-total vaccination serum HI SPR in the population of <40 before vaccination, and the 28d post-total vaccination serum HI SPR in the population of ≥ 40 before vaccination under the H1N1 and H3N2 types in test group 1, test group 2, and pooled control group will be analyzed using the same statistical methods as those used for post-vaccination SPR.

If the lower limit of the two-sided 95%CI for the 28d post-total vaccination serum HI SPR of the test group for this type is $\geq 60\%$, this type has reached the absolute standard for SPR.

✧ GMT and GMI analysis

In PPS analysis, the covariance analysis model will be employed to analyze the antibodies under H1N1 and H3N2 types, respectively. After logarithmic transformation, the serum HI GMT 28d post-vaccination will be fitted to the covariance analysis model for analysis, with the serum HI GMT 28d post-vaccination after logarithmic transformation as a dependent variable of the model, the logarithmic transformation value of pre-vaccination serum HI antibody GMT as a covariate of the model, and groups will be the fixed effect in the model. The post-vaccination logarithmic transformation value of each group and the least square mean of the difference between groups will be calculated based on the

model. After inverse logarithmic transformation, the post-vaccination antibody corrected geometric mean based on the least square mean of each group, the corrected ratio between groups (test group 1/pooled control group), (test group 2/pooled control group), (test group 1/test group 2), and their 95%CIs will be calculated.

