In the mFAS and FAS analyses, the missing data in 28d post-total vaccination serum HI antibody will be imputed using the multiple imputation method, and each imputed dataset will be statistically analyzed using the same covariance analysis model as in the PPS analyses. The analytical results of the imputed datasets will be pooled using Rubin's method and inverse-logarithmically transformed to obtain the corrected GMT for each group, corrected GMT ratio between each pair of groups, and corresponding 95%CIs.

If the lower limit of the two-sided 95%CI for (test group 1/pooled control group) and (test group 2/pooled control group) is $\geq 2/3$, the post-vaccination antibody GMT of the test group for this type is considered to be non-inferior to that of the pooled control group. Otherwise, the non-inferiority test is considered to have failed.

The same method as mentioned above will be adopted to perform a logarithmic transformation on the GMT of serum HI antibody in the susceptible population 28d post-total vaccination, and then fit the covariance analysis model for analysis.

Meanwhile, in the PPS analysis, all population, susceptible population, non-susceptible population, population of <40 before vaccination and population of ≥ 40 before vaccination under the H1N1 and H3N2 types in the test group 1, test group 2, and pooled control group will be statistically described in terms of HI antibody GMT and GMI, respectively, and the group differences will be statistically examined by using the ANOVA with logarithmic transformation. Meanwhile, the 28d post-total vaccination antibody's GMT/GMI ratio and corresponding 95%CIs will be calculated for the two groups, and the inter-group difference will be statistically tested by t-test after logarithmic transformation.

In the mFAS and FAS analyses, the missing data in the post-vaccination antibodies will be imputed using the multiple imputation method, and each imputed dataset will be statistically analyzed using the same method as in the PPS analysis. The analytical results of the imputed datasets will be pooled using Rubin's method and inverse-logarithmically transformed to obtain the GMT for each group, the GMI for each group, the GMT ratio between each pair of groups, the GMI ratio between each pair of groups, as well as their corresponding 95%CIs.

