- ✓ If the lower limit of the two-sided 95%CI of SCR difference for 28d post-total vaccination serum HI antibody between the two groups (test group 1-control group 1) and (test group 2-control group 1) for this type is $\geq -10\%$, the post-vaccination SCR of the test group for this type can be considered to be non-inferior to that of the control group 1. Otherwise, the non-inferiority test is considered to have failed.

✧ **Analysis of post-vaccination antibody SPR**

The post-vaccination antibody SPR in all populations, 28d post-total vaccination serum HI SPR in the susceptible population, and the 28d post-total vaccination serum HI SPR in the non-susceptible population, and the 28d post-total vaccination serum HI SPR in the population of <40 before vaccination, and the 28d post-total vaccination serum HI SPR in the population of ≥ 40 before vaccination under the H1N1 and H3N2 types in test group 1, test group 2, control group 1 and control group 2 will be analyzed using the same statistical methods as those used for post-vaccination SPR. If the lower limit of the two-sided 95%CI for the 28d post-total vaccination serum HI SPR of the test group for this type is $\geq 60\%$, this type has reached the absolute standard for SPR.

✧ **GMT and GMI analysis**

In PPS analysis, the covariance analysis model will be employed to analyze the antibodies under the BV type in the test group 1, test group 2, control group 1, and control group 2, respectively. After logarithmic transformation, the serum HI GMT 28d post-vaccination will be fitted to the covariance analysis model for analysis, with the serum HI GMT 28d post-vaccination after logarithmic transformation as a dependent variable of the model, the logarithmic transformation value of pre-vaccination serum HI antibody GMT as a covariate of the model, and groups will be the fixed effect in the model. The post-vaccination logarithmic transformation value of each group and the least square mean of the difference between groups will be calculated based on the model. After inverse logarithmic transformation, the post-vaccination antibody corrected geometric mean based on the least square mean of each group, the corrected ratio between groups (test group 1/control group 1), (test group 2/control group 1), (test group 1/control group 2), (test group 2/control group 2) and (test group 1/test group 2) and their 95%CIs will be calculated.

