In the mFAS and FAS analyses, the missing data in 28d post-total vaccination serum HI antibody will

be imputed using the multiple imputation method, and each imputed dataset will be statistically analyzed using the same covariance analysis model as in the PPS analyses. The analytical results of the imputed datasets will be pooled using Rubin's method and inverse-logarithmically transformed to obtain the corrected GMT for each group, the corrected GMT ratios between each pair of groups, and corresponding 95% CIs.

If the lower limit of the two-sided 95%CI for (test group 1/control group 1) and (test group 2/control group 1) is $\geq 2/3$, the post-vaccination antibody GMT of the test group for this type is considered to be non-inferior to that of the pooled control group. Otherwise, the non-inferiority test is considered to have failed.

Meanwhile, in the PPS analysis, all population, susceptible population, non-susceptible population, population of <40 before vaccination and population of ≥ 40 before vaccination under the BV type in the test group 1, test group 2, control group 1 and control group 2 will be statistically described in terms of HI antibody GMT and GMI, respectively, and the group differences will be statistically examined by using the ANOVA with logarithmic transformation. Meanwhile, the 28d post-total vaccination antibody's GMT/GMI ratio and corresponding 95% CIs will be calculated for the two groups, and the inter-group difference will be statistically tested by t-test after logarithmic transformation.

In the mFAS and FAS analyses, the missing data in the post-vaccination antibodies will be imputed using the multiple imputation method, and each imputed dataset will be statistically analyzed using the same method as in the PPS analysis. The analytical results of the imputed datasets will be pooled using Rubin's method and inverse-logarithmically transformed to obtain the GMT for each group, the GMI for each group, the GMT ratio between each pair of groups, the GMI ratio between each pair of groups, as well as their corresponding 95% CIs.

The reverse cumulative distribution of antibody titers for BV will be generated separately for test group 1, test group 2, control group 1, and control group 2.

(3) An intergroup comparison of non-inferiority for BY is made between test groups and control groups.

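### Do the non-inferiority rules in SAP 6.8 require both doses to pass together, against the 0.5 mL-first sequence?

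*SAP*

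**What the plan says.** **Sequence.** Protocol 7.1.2, repeated in SAP 4.3, orders the two doses: "First, test group 2 is evaluated. If the positive conclusion of test group 2 is established, test group 1 is further evaluated". Test group 2 is 0.5 mL and test group 1 is 0.25 mL. SAP 4.3 rests its multiplicity position on that order: "Therefore, class I error correction is no longer carried out".

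**Decision rules.** SAP 6.8 prints four non-inferiority rules:
- H1N1/H3N2 seroconversion: "test group 1-pooled control group) and (test group 2-pooled control group) for this type", lower limit at least −10%.
- H1N1/H3N2 GMT: "If the lower limit of the two-sided 95%CI for (test group 1/pooled control group) and (test group 2/pooled control group) is" at least 2/3.
- B/Victoria seroconversion: "test group 1-control group 1) and (test group 2-control group 1) for this type is" at least −10%.
- B/Victoria GMT: "If the lower limit of the two-sided 95%CI for (test group 1/control group 1) and (test group 2/control group 1) is" at least 2/3.

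Each ends with the same clause: "Otherwise, the non-inferiority test is considered to have failed". None mentions an order or refers to 4.3. B/Yamagata follows the B/Victoria method, but its text names test group 1 or test group 2.

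**Dose ratio.** The secondary objective, Secondary Estimand 1 and Protocol 7.2 ask whether 0.5 mL is non-inferior to 0.25 mL. SAP 6.8 lists the adjusted ratio as test group 1 over test group 2.

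**The concern.** The four rules join the two dose contrasts with a plain conjunction and give one undivided failure outcome. Taken literally, non-inferiority holds for a strain only if both doses meet the limit, so a 0.25 mL failure would remove a 0.5 mL claim that SAP 4.3 would allow.

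The two readings part in one case only: 0.5 mL passes and 0.25 mL does not. The 0.25 mL verdict is the same either way, since under the sequence it also needs 0.5 mL to succeed first. The literal reading is the stricter one, so type I error is not at issue. What would be at stake is the 0.5 mL verdict when 0.25 mL is weak. That case is not far-fetched: Protocol 2.4 cites B/Victoria GMTs of 64.0 for a 0.25 mL quadrivalent vaccine and 91.3 for the trivalent.

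The dose ratio raises a smaller worry. A lower-limit rule of 2/3 applied to the ratio as printed would test the opposite claim.

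**Working it through.** **1. The plan's sample size is per dose.** Inputs from SAP 4.3: seroconversion 65% in both arms, margin −10%, one-sided α 0.025, power 96% per strain; GMT margin −0.176 and SD 0.7 on the log scale, power 99% per strain.
- A restricted-likelihood score test gives 914/457 at 2:1 and 625 per group at 1:1, matching the plan exactly.
- For GMT, a t-based calculation gives 874/437, and the normal formula gives 582 at 1:1. Both match.
- Type II error is 0.16 over four strains for seroconversion and 0.04 over four strains for GMT: 4 × 0.04 + 4 × 0.01 = 0.20. That uses the whole allowance on one test group. Nothing is set aside for a second dose that must pass at the same time.

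**2. What the literal reading would cost.** Take 914 per dose, 457 per trivalent arm, 914 pooled, all arms equal, endpoints independent. Power per test = Φ(margin/SE − 1.96):

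| Test | SE | Power |
|---|---|---|
| Seroconversion, A strains | √(0.65×0.35×2/914) = 0.0223 | 0.994 |
| Seroconversion, B strains | √(0.65×0.35×(1/914+1/457)) = 0.0273 | 0.955 |
| GMT, A strains | 0.7×√(2/914) = 0.0327 | 0.9997 |
| GMT, B strains | 0.7×√(1/914+1/457) = 0.0401 | 0.992 |

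There are two strains in each row, so the chance that 0.5 mL passes all eight tests is 0.994² × 0.955² × 0.9997² × 0.992² ≈ 0.888.

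Requiring 0.25 mL to pass as well needs simulation, because the doses share controls (300,000 runs):

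| True 0.25 mL / trivalent GMT ratio, B/Victoria only | 0.5 mL alone | Joint on A strains and B/Victoria | Joint on all strains |
|---|---|---|---|
| 1.00 (planning value) | 0.888 | 0.847 | 0.816 |
| 0.90 (assumed) | 0.888 | 0.771 | 0.743 |
| 0.80 (assumed) | 0.888 | 0.434 | 0.419 |
| 0.70 (64.0/91.3) | 0.888 | 0.067 | 0.065 |

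At planning values the readings disagree in 0.888 − 0.847 = 4% to 0.888 − 0.816 = 7% of trials, and the joint reading stays above the stated 80%. With no dropout (1,100/550) the three figures are 0.954, 0.936 and 0.920. The absolute criteria are passed with probability above 0.999 at n = 914 and do not alter these figures. The last three rows are illustrations; the 0.70 ratio comes from unadjusted GMTs in another study.

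**3. Which reading the documents support.**
- SAP 4.3 and Protocol 7.1.2 reach a positive conclusion for 0.5 mL before 0.25 mL is looked at. Under the joint reading 0.5 mL could not succeed unless 0.25 mL had already passed non-inferiority, so the stated order would do almost nothing.
- SAP 6.7 states each non-inferiority hypothesis as one test-group rate or GMT against one control. None is a joint hypothesis over two doses.
- SAP 3.1.1 has a separate primary objective for each dose; the 0.25 mL one reads "after 2 doses of 0.25mL quadrivalent influenza vaccine (0.25mL-dose QIV) compared with two trivalent influenza vaccines (including BV or BY) for the shared strains".
- The primary estimand treats the test group as 0.5 mL or 0.25 mL.
- The B/Yamagata text in 6.8 names one test group or the other, and the sensitivity analyses in 6.10 run test group 1 and then repeat for test group 2.
- The 6.8 rules themselves conclude about a single test group.

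**4. The dose ratio.** A lower limit of at least 2/3 for test group 1 over test group 2 equals an upper limit of at most 1.5 for the ratio in the protocol direction. With 914 per arm the half-width is 1.961 × 0.7 × √(2/914) = 0.0642 log10. The two directions therefore disagree only if the observed 0.5/0.25 ratio is above 10^(0.1761 − 0.0642) = 1.29 or below 1/1.29 = 0.77. At an assumed true ratio of 1.2 the wrong direction passes 84% of the time, and at 1.3, 48%; the protocol direction passes more than 99.9% at both. These figures describe an error that the SAP does not instruct: 6.8 lists this ratio for estimation and attaches no limit to it.

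**The case for a change.** The best case for acting is that a confirmatory decision rule should have one reading before unblinding. Settling it afterwards, in the one situation where the readings differ, could look driven by the result. The 6.7 hypotheses say only the test group and do not name the dose; B/Yamagata is worded one way while borrowing a rule worded another; and a clarification would cost a few words.

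What stands is that the wording is loose, as it is elsewhere in this translated SAP: the B/Victoria GMT rule, for example, concludes about the pooled control although its contrast is with control group 1. What does not stand is that the decision is open. The order is already fixed in writing in both documents, so an analyst who judges 0.5 mL on its own limits is following the plan and not choosing after the fact. The large losses in the table need both the unsupported reading and an assumed weak 0.25 mL dose.

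The body of SAP 6.11 Multiplicity is not visible in the text reviewed, and Protocol 9.11 was not translated. Nothing is inferred from either.

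**Conclusion.** The concern does not call for a change. The four rules in SAP 6.8 are compressed statements of one test per dose, to be applied in the order of SAP 4.3, and the rest of the plan is consistent only with that reading. Under it the 0.5 mL non-inferiority claim keeps its planned power (about 89% at 914/457, assuming equal arms and independent endpoints), and rewording the rules would alter no estimate, interval or conclusion. The joint reading would cost 4 to 7 percentage points at planning values and far more if 0.25 mL were truly weaker, but it would make the explicit sequence pointless.

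The reversed dose ratio is a clerical matter. Its interval inverts exactly, and Protocol 7.2 together with the secondary objective fixes direction and margin, with SAP 2.3 declaring no departure from the protocol. Each dose's contrasts with control are reported under either reading, so a reader can check every verdict.

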Susceptible population: HI antibody titer $<1:10$ before immunization

Non-susceptible population: HI antibody titer $\geq 1:10$ before immunization

Seroconversion: HI antibody titer $<1:10$ before immunization, and the antibody titer $\geq 1:40$ after immunization, or

HI antibody titer $\geq 1:10$ before immunization, and the antibody titer after immunization increased ≥ 4 folds.

Protection: HI antibody titer $\geq 1:40$ as the limit of protective antibody

Table 3.2.1.2 Intercurrent Events and Treatment Strategies of Primary Estimand

3.2.2 Secondary Estimand 1

Table 3.2.2.1 Secondary Estimand 1

Secondary Estimand 1	
Population	The target population involves all participants aged 6 to 35 months who have completed two doses of vaccination.
Variable	(1) Whether the H1N1, H3N2, BV, and BY HI antibodies are seroconverted in both the test group 2 (0.5mL) and the test group 1 (0.25mL) 28 days after the second dose. (2) H1N1, H3N2, BV, and BY serum HI antibody titers of the test group 2 (0.5mL) and the test group 1 (0.25mL) 28 days after the second dose.
Treatments	As the same as the primary estimand
Intercurrent Events and Treatment Strategies	As the same as the primary estimand
Population-level Summary	(1) Difference between the SCRs of H1N1, H3N2, BV, and BY serum HI antibodies of the test group (0.5mL) and the test group (0.25mL) 28 days after the second dose. (2) GMT ratios of H1N1, H3N2, BV, and BY serum HI antibodies between the test group (0.5mL) and the test group (0.25mL) 28 days after the second dose.

3.2.3 Secondary Estimand 2

Table 3.2.3.1 Secondary Estimand 2

Secondary Estimand 2	
Population	The target population involves all participants aged 6 to 35 months who have completed two doses of vaccination.
Variable	
(1) Whether the BV HI antibody is seroconverted in the test group (0.5mL or 0.25mL) and the TIV-BY group 28 days after the second dose.
 
(2) Whether the BY HI antibody is seroconverted in the test group (0.5mL or 0.25mL) and the TIV-BV group 28 days after the second dose.

Secondary Estimand 2	
	(3) BV HI antibody titers of the test group (0.5mL or 0.25mL) and the TIV-BY group 28 days after the second dose. (4) BY HI antibody titers of the test group (0.5mL or 0.25mL) and the TIV-BV group 28 days after the second dose.
Treatments	As the same as the primary estimand
Intercurrent Events and Treatment Strategies	As the same as the primary estimand

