6.1.5 Table and Listing

➤ **Table**

Results will be generally summarized by groups (including test group 1, test group 2, control group 1, and control group 2). Groups are generally presented in the form of columns, and the specific group display will be adjusted according to the actual situation.

➤ **Listing**

Unless otherwise specified, all listings will include group, site, subject number, and the original data will be displayed first. The listing will be generally sorted in sequence by group, site, subject number, visit, or other relevant times (such as the start date of AE).

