6.3 Demographic and Baseline Characteristics

Descriptive statistics will be performed separately for the following demographic data and baseline characteristics, including age(in months), gender, ethnicity, body length/height, weight, and pre-vaccination axillary temperature.

Based on the distributional characteristics of the variables, ANOVA will be used to statistically compare between-group differences in age, body length/height, weight, and pre-vaccination axillary temperature. The Chi-square test or Fisher's exact test will be used to statistically compare between-group differences in gender and ethnicity. Demographic data and baseline characteristics will be listed. The previous severe medical history and current medical history will be encoded using MedDRA version 26.1 or higher. The number of subjects and incidence rates of previous severe medical history/current medical history will be calculated, respectively, according to the SOC and PT grades, and Fisher's exact test will be used to statistically test the differences in the frequency of previous severe medical history/current medical history between groups. All medical history will be listed.

The above analysis is based on mFAS, FAS, and PPS.

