6.8 Immunogenicity Evaluation

Immunogenicity analysis will be based on mFAS, PPS, and FAS. The analysis based on the FAS will not take into account the intercurrent events "early discontinuation of treatment due to loss of visits, withdrawal of informed consent, etc., and failure to complete the full-course vaccination". In addition, if the antibody test result is " $<1:10$ ", it is counted as "5". If the antibody test result is " $>1:10240$ ", it is counted as "10241".

(1) Immunogenicity will be compared between the test group and a pooled trivalent control group of two different sizes for H1N1 and H3N2 types, respectively.

✧Analysis of post-vaccination SCR

In the PPS analysis, the 28d post-total vaccination serum HI SCR in all populations, the 28d post-total vaccination serum HI SCR in the susceptible population, and the 28d post-total vaccination serum HI SCR in the non-susceptible population will be calculated in the test group 1, test group 2, and pooled control group under the H1N1 and H3N2 types, respectively, and the two-sided 95%CIs will be calculated using the Clopper-Pearson method. Meanwhile, the Miettinen & Nurminen method will be used to calculate the two-sided 95%CI of the inter-group rate difference, and the Chi-square test/Fisher's exact test will be used for the statistical test of inter-group difference.

In the mFAS and FAS analyses, multiple imputation methods will be used to impute in the missing data in the post-vaccination antibodies, and the 28d post-total vaccination serum HI SCR in all populations, the 28d post-total vaccination serum HI SCR in the susceptible population, and the 28d post-total vaccination serum HI SCR in the non-susceptible population will be calculated for all populations in the test group 1, test group 2, and combined control group under the H1N1 and H3N2 types, respectively based on the imputed datasets. The analysis results of pooled post-imputed datasets will be pooled using Rubin's method to obtain the pooled SCR, the difference in rates between the two groups, and their 95%CIs for each group. If the CI for pooled rate or rate difference is not estimable, the rate or rate difference and its 95%CI will be estimated using the Bootstrap method, which will be sampled 1,000 times with putbacks and seeded = 111.

- ✓ If the lower limit of the two-sided 95%CI for the 28d post-total vaccination serum HI SCR of the test group for this type is $\geq 30\%$, this type has reached the absolute standard for SCR.

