Immunogenicity will be compared between the test group (test group 1 or test group 2) and control group 2 for BY types, respectively, using the same method as for BV types.

Forest plots of the SCR, SPR, and GMT of HI antibody of each serotype in all populations 28d post-total vaccination will be plotted.

Sensitivity Analysis: In mFAS analysis, the missing data in the serum HI antibody and SCR of HI antibody 28d post-total vaccination will be analyzed for sensitivity analysis by using the Tipping Point Analysis (TPA) and the Jump to Reference (J2R) method based on δ adjustment. Evaluate the robustness impact of missing data on the test results. For details, please refer to Section 6.10 on the handling of Missing Data.

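### Age enters neither co-primary analysis and baseline serostatus does not stratify the overall SCR difference; using both would be a small, cheap gain in precision

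*SAP*

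**What the plan says.** **SCR.** In the per-protocol analysis (SAP 6.8), "the Miettinen & Nurminen method will be used to calculate the two-sided 95%CI of the inter-group rate difference". No stratum or covariate is named. The text is the same for H1N1/H3N2 (pooled control) and for BV, and BY is analysed "using the same method as for BV types".

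**GMT.** The ANCOVA in SAP 6.8 has treatment as its only factor ("groups will be the fixed effect in the model"). Its single covariate is the baseline titre, on the log scale. Nothing else enters. The mFAS and FAS analyses fit the same model after multiple imputation.

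**What is recorded.**
- SAP 6.3 summarises baseline data "including age(in months), gender, ethnicity, body length/height, weight, and pre-vaccination axillary temperature".
- SAP 6.1.5 says that "all listings will include group, site, subject number".
- SAP 3.2.1 gives "Susceptible population: HI antibody titer $<1:10$ before immunization", with non-susceptible as the complement. SAP 6.8 reports SCR in both subgroups, and Secondary Estimand 3 covers the susceptible children.

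**Randomization.** Protocol 7.5.1 and SAP 4.2 mention preset block lengths and no stratification factor. Further detail is left to a separate randomization document.

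**The concern.** The population runs from 6 to 35 months at several centres, and both age and pre-existing antibody could plausibly predict the response. Adjusting for prognostic baseline variables narrows the interval for the treatment comparison and removes the effect of chance imbalance. The plan does this for GMT through baseline titre. It does not do it for SCR, although seroconversion is itself defined by different rules below and at or above 1:10.

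The SCR comparison on the B strains is where precision is scarcest. It sets the sample size (914/457) and is planned at 96% power per strain, against 99% for GMT. What is at stake is some precision that could be had from data already collected. The validity of the result is not in question.

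**Working it through.** **Inputs (SAP 4.3).** One-sided alpha 0.025; SCR 65% in both arms; margin -10 points; 2:1 allocation for B strains; 96% power per SCR test. For GMT: log10 margin -0.176, SD 0.7, 99% power.

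**Step 1: reproduce the plan's figures.** The Farrington-Manning score formula, which is the sample-size counterpart of Miettinen-Nurminen, gives 457 control and 914 test (2:1) and 625 per group (1:1). All match the stated figures. For GMT, the noncentral-t calculation gives 437 controls at 2:1, and the normal approximation gives 582 per group at 1:1, as stated.

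**Step 2: SCR power on a B strain, unadjusted.** The rates constrained to a difference of -10 points are 0.6133 (test) and 0.7133 (control).
- Null SE = sqrt(0.6133 × 0.3867/914 + 0.7133 × 0.2867/457) = 0.02659
- Alternative SE = sqrt(0.65 × 0.35 × (1/914 + 1/457)) = 0.02733
- Power = Φ((0.10 - 1.960 × 0.02659)/0.02733) = Φ(1.752) = 96.0%

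**Step 3: SCR power with adjustment.** If baseline variables explain a share R² of the outcome variance, both SEs are multiplied by sqrt(1 - R²). The documents give no R², so these values are assumptions.

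| Assumed R² | Null SE | Alternative SE | Power per B-strain SCR test |
|---|---|---|---|
| 0 | 0.02659 | 0.02733 | 96.0% |
| 2% | 0.02632 | 0.02705 | 96.3% |
| 5% | 0.02592 | 0.02663 | 96.8% |
| 10% | 0.02522 | 0.02592 | 97.4% |

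Controls needed for 96% power fall from 457 to 448, 434 and 411 at R² of 2%, 5% and 10%.

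**Step 4: what such an R² would mean.** For a two-level factor with a share f in one level and an SCR gap g, R² = g² × f × (1 - f)/(0.65 × 0.35). With f = 0.5, a gap of 20 points gives 0.04 × 0.25/0.2275 = 4.4%, and a gap of 30 points gives 9.9%. Both gaps are illustrations.

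**Step 5: GMT.** Take 0.7 as the residual SD, since the SAP does not say whether it is before or after adjustment for baseline titre. At 914/457, SE = 0.7 × sqrt(1/914 + 1/457) = 0.0401 and power = Φ(0.176/0.0401 - 1.960) = 99.2%. If age explains a further 2%, 5% or 10% of the variance, power is 99.3%, 99.4% or 99.6%.

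**Step 6: overall power.** H1N1 and H3N2 use the pooled control, and 914 v 914 gives 99.4% SCR power. Summing the type II errors of the eight non-inferiority tests for one test group, at the sizes above and with no adjustment:
- B-strain SCR 0.080
- A-strain SCR 0.011
- B-strain GMT 0.015
- A-strain GMT 0.001

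Overall non-inferiority power is therefore at least 1 - 0.107 = 89.3%, against a target of 80%. With R² of 2-10% throughout, the bound becomes 90.3-93.5%.

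**The case against.** The strongest reply is that nothing here needs repair. The two-group interval is valid, agrees with the method behind 914/457, and matches Protocol 7.2, which asks for an adjusted GMT ratio but only for an SCR difference. Under the plan's own assumptions the non-inferiority power already exceeds its target. All of this stands, and it limits the point to an optional improvement.

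Three stronger readings are tempting, and the documents do not support them:
- **That baseline serostatus goes unused.** Log baseline titre is already in the GMT model, and serostatus is only a dichotomy of it. Serostatus also defines the SCR subgroups and Secondary Estimand 3. What is missing is its use as a stratifier of the overall SCR difference.
- **That randomization is unstratified, so age and site are uncontrolled.** The documents only fail to state any stratification; the detail sits in a document not available here. Protocol 9.11 is also untranslated, so only the SAP text can be checked.
- **That site should simply be added throughout.** The number of centres is not given, and sparse site terms cannot be ruled out.

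It is also fair to say that stratification brings choices. If the SCR difference varies by stratum, the weights determine which overall difference is held against -10%. The imputation and sensitivity analyses in SAP 6.8 and 6.10 would need a matching rule. These are reasons to specify the change carefully, not reasons against it.

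**Conclusion.** The point holds as an efficiency improvement of low priority. Age is used in neither co-primary analysis, and serostatus does not stratify the overall SCR difference. In the GMT model only age, and possibly site, is left unused. The gain is about 0.3 to 1.4 percentage points of power per B-strain SCR test and less than one point for GMT. It rests on an assumed R² of 2-10% for age and serostatus together (age alone for GMT) and on the plan's 65% SCR in both arms.

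The gain would be larger if the true SCR on a B strain were lower with QIV. Protocol 2.4 raises lower B-strain titres but gives no SCR gap. Under an assumed true difference of -2 points, the same score calculation gives 84.1% power unadjusted, and 85.8% or 87.6% at R² of 5% or 10%. That scenario is an illustration, not a forecast.

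**What to change.** Make the change before unblinding. Protocol 7.5.5 places unblinding once the post-dose-2 serology is available, which can precede final database lock. If that point has passed, report the adjusted results as supplementary only.

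1. **GMT:** add age in months to the ANCOVA beside log baseline titre for all four strains. Add site only if centres are large enough, or after pooling small ones by a stated rule.
2. **SCR (primary per-protocol difference):** use a stratified Miettinen-Nurminen interval. The strata are strain-specific baseline titre (<1:10, ≥1:10) by age band (6-11, 12-23, 24-35 months). Pre-specify the weights, for example proportional to stratum size, so that the target stays the overall difference. State how sparse strata are merged. Keep the -10% margin and report the unstratified interval as supportive.
3. **Imputed analyses:** state whether the mFAS/FAS analyses and the sensitivity analyses in SAP 6.10 use the same strata or stay unstratified.
4. **Consistency:** revisit the statement in SAP 2.3 that nothing departs from the protocol's analyses.

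The cost is SAP wording, slightly more programming, and a primary SCR interval that is a little less simple. No new data or participants are needed.
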